We estimate that 25% of screened patients will not meet eligibility criteria, which means that at least 300 patients will be screened.

d) Study Timelines

Subjects will be enrolled during their hospital stay and will participate in the study for 3 months following hospital discharge. The intervention will be delivered during the 4 weeks following discharge. Final assessment for outcomes will be performed at 3 months after discharge. We anticipate enrollment will occur between July and December of 2019. We estimate that primary analyses will be completed by June of 2020.

e) Study Endpoints

The primary outcome will be the number of initial hospital readmissions within 30 days of discharge. Secondary outcomes will also be assessed at 30 days of discharge unless otherwise specified. Secondary outcomes will include:

1. time to first readmission
2. number of emergency department (ED) visits
3. a composite of 30d readmissions and ED visits

Readmission Pilot Trial

4. number of primary care and specialist provider follow-up visits scheduled and attended
5. incidence of medication review or reconciliation post-discharge
6. cost of post-discharge care as a sum of ED visits, readmission, home health services, and outpatient provider visits
7. cost of the intervention
8. subject experience assessed by a brief questionnaire
9. self-monitored blood glucose levels and frequency of testing
10. change in well-being from baseline to 5 weeks after discharge as measured by the World Health Organization Well-Being Index (WHO-5).[43]
11. change in diabetes-related distress at 5 weeks after discharge as measured by the Problem Areas in Diabetes (PAID) scale.[44]
12. change in perceived social support at 5 weeks after discharge as measured by the Multidimensional Scale of Perceived Social Support (MSPSS).[45]
13. change in perceived stress at 5 weeks after discharge as measured by the perceived stress scale (PSS).[46]
14. change in diabetes knowledge at 5 weeks after discharge as measured by the Diabetes Knowledge Test (DKT2).[47]
15. change in A1c level from baseline to 3 months after the index discharge

f) Procedures Involved in the Human Research

After enrollment, subjects will be sorted into 2 groups based on the predicted risk of readmission by the DERRI: high risk and low risk (Figure 1).

[figure not shown]

Figure 1. Allocation of study participants

Low-risk group:

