The **low-risk group** will be followed in a prospective, observational arm of the study. About 5 weeks after hospital discharge, the Temple medical record will be reviewed for the presence of any hospital or ED visits within 30 days after discharge. If no post-discharge acute visits are found, then the subject will be contacted to determine if any hospital or ED visits occurred at another institution.

- The following data will be collected at baseline: sociodemographics, medical history, including HIV, substance abuse, and mental health status, which are likely risk factors for admission, relevant laboratory results, admission diagnoses, well-being (WHO-5), diabetes-related distress (PAID scale), perceived social support (MSPSS), perceived stress (PSS), diabetes knowledge (DKT2), depression screening by the 2-item Patient Health Questionnaire (PHQ-2), [48] and health literacy by the Brief Health Literacy Scale (BHLS). [49, 50] Subjects who score 3 or more on the PHQ-2 will complete the PHQ-9. [51] Subjects with a PHQ-9 score of 5 or more will be referred to their primary care physician (PCP) for evaluation and management of possible depression. [52] For subjects without a PCP, a study physician will begin medical therapy for depression as needed. For subjects newly discovered to be suicidal, psychiatry will be consulted in the hospital.
- The following data will be collected during follow-up: A1c, discharge diagnoses, hospital readmission (date, primary diagnosis), ED visits (date, primary diagnosis) and patient experience according to a brief questionnaire (Appendix Item 3a).

High-risk group:

For the **high-risk group**, there are two phases in the protocol. Phase A is the pilot RCT to explore the feasibility, acceptability, and efficacy of the intervention. Phase B consists of in-depth interviews with intervention participants and research staff to further explore acceptability and effects of the intervention and to refine the protocol for future study. Subjects in the high-risk group will be randomly assigned with a computer-generated randomization scheme 1:1 in randomly permuted blocks of 2, 4, or 6 to receive either the intervention, the Diabetes Transition of Hospital Care (DiaTOHC) Program (“My Temple Extra Care Service”) or usual care (control).

Phase A: RCT of readmission risk reduction intervention

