≤ 10 U	Decrease by 1 U	Increase by 1 U
>11- 19 U	Decrease by 2 U	Increase by 2 U
≥ 20 U	Decrease by 3 U	Increase by 3 U
Pre-meal Dose, U	BG 40-70 mg/dl x 1	BG 180-240 mg/dl x 1

Readmission Pilot Trial

≤ 10 U	Decrease by 2 U	Increase by 2 U
>11- 19 U	Decrease by 3 U	Increase by 3 U
≥ 20 U	Decrease by 4 U	Increase by 4 U
Pre-meal Dose, U	BG < 40 mg/dl x 1***	BG > 240 mg/dl x 1
≤ 10 U	Decrease by 4 U	Increase by 3 U
>11- 19 U	Decrease by 6 U	Increase by 4 U
≥ 20 U	Decrease by 8 U	Increase by 5 U

Pre-meal insulin dose adjustment is based on the subsequent BG value, e.g., pre-breakfast insulin dose is based on the pre-lunch BG.

* If > ½ of the mealtime/HS BG values for the week were below target.

**If > ½ of the mealtime/HS BG values for the week were above target.

*** Decrease by 30-40% in the event of severe hypoglycemia (mealtime/HS BG < 40 mg/dl).

BG=blood glucose; Mealtime/HS=pre-lunch, pre-dinner, or bedtime

The above algorithm provides recommended insulin doses and may be modified based on clinical judgment of the investigator or co-investigator.

Usual care: Most aspects of the intervention go above-and-beyond usual care. Patients in the usual care group will receive the standard discharge instructions and medication reconciliation process. Those who are new to diabetes receive training by a floor nurse on using a glucometer as well as a stock set of printed educational materials. The floor nurses also train patients who are new to insulin injections as needed. Patients with diabetes are referred to outpatient diabetes education at Temple on a case-by-case basis as determined by the primary hospital provider team. Diabetes therapy upon discharge is decided on a case-by-case basis by the primary team. Discharge instructions are routinely sent to the primary care physician either by fax or EPIC. Most TUH patients receive a phone call 2 to 4 days after discharge from a CHW that includes checking on the status

Table 2. Timeline for assessments of subjects

Visit #	1	2	3	4	5	6	7	8
Time (weeks)	0	2 days	1	2	3	4	5	13
Intervention group								
Phone call/clinic visit								X
Psychometric assessments	X							X
Diabetes knowledge	X							X
30d endpoints								X
Interview							X	
A1C	X							X
Navigator call		X	X	X	X	X		
Blood glucose		X	X	X	X	X	X	
Adverse events		X	X	X	X	X	X	
Usual care group								
Phone call								X
Psychometric assessments	X							X
Diabetes knowledge	X							X
30d endpoints								X
A1C	X							X
Blood glucose								X

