Adverse events								X
Low-risk group								
Chart review/phone call								X
Psychometric assessments	X							X
Diabetes knowledge	X							X
A1C	X							X
30d endpoints								X

Readmission Pilot Trial

of follow-up appointments, confirming access to medications, and answering questions.

Data collection: The following data will be collected at baseline: A1c, sociodemographics, medical history, including HIV, substance abuse, and mental health status, which are likely risk factors for admission, relevant laboratory results, admission diagnoses, self-reported goals for health and diabetes, well-being (WHO-5), diabetes-related distress (PAID scale), perceived social support (MSPSS), perceived stress (PSS), diabetes knowledge (DKT2), depression screening by the PHQ-2/9, and health literacy by the BHLS (Table 2).

The following data will be collected during follow-up: A1c, discharge diagnoses, hospital readmission (date, primary diagnosis), ED visits (date, primary diagnosis), physician follow-up appointments scheduled and/or attended, post-discharge medication reconciliation (yes/no), cost of post-discharge care, self-monitored blood glucose levels, Nurse Navigator time to deliver the intervention (minutes), well-being (WHO-5), diabetes-related distress (PAID scale), perceived social support (MSPSS), perceived stress (PSS), diabetes knowledge (DKT2), depression (PHQ), and patient experience according to a brief questionnaire (**Appendix Item 3a [usual care] or 3b [intervention]**). These follow-up data will be collected during a phone call about 5 weeks after the index discharge. Baseline and 3-month post-discharge A1c levels will be obtained as part of standard-of-care. A letter reminding patients to do the 3-month blood draw for the A1c test will be sent by mail.

Data will be collected by phone interviews with subjects and review of the electronic medical record (EMR). The Research Specialist will be primarily responsible for screening and recruiting subjects, data collection and data entry.

Phase B: Qualitative evaluation of intervention

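### Table 2 puts the follow-up call, questionnaires, diabetes knowledge test and ascertainment of 30-day events at week 13, where the protocol text puts them at about 5 weeks

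*Protocol*

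**What the plan says.** Section 8(e), Study Endpoints, sets five secondary outcomes (10 to 14: WHO-5, PAID, MSPSS, PSS and DKT2) at 5 weeks. Outcome 11, for example, is "change in diabetes-related distress at 5 weeks after discharge as measured by the Problem Areas in Diabetes (PAID) scale". Outcome 15, the change in A1c, is the only one set at 3 months. Readmission and ED outcomes refer to the 30 days after discharge.

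Section 8(f), Data collection (Phase A, the randomised arms), lists readmissions, ED visits, self-monitored glucose, the questionnaires and the DKT2, and then states: "These follow-up data will be collected during a phone call about 5 weeks after the index discharge". The 3-month A1c is a standard-of-care blood test prompted by a mailed letter.

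Section 8(f), Low-risk group, says: "About 5 weeks after hospital discharge, the Temple medical record will be reviewed for the presence of any hospital or ED visits". Subjects with no acute visit on record are then contacted about visits elsewhere.

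The schedule, headed "Table 2. Timeline for assessments of subjects", has eight visit columns, with visit 7 at week 5 and visit 8 at week 13. In every group the rows "Psychometric assessments" and "Diabetes knowledge" are marked at weeks 0 and 13, and "30d endpoints" at week 13 only. The follow-up call or chart review is also at week 13 only.

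Section 8(d), Study Timelines, adds: "Final assessment for outcomes will be performed at 3 months after discharge".

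**The concern.** The assessment schedule and the endpoint definitions give different times for the same measurements. For the five change scores, the time point is part of the endpoint. Navigator calls end at week 4, so a week-5 score describes the effect about 1 week after support stops, and a week-13 score the effect 9 weeks after. These are different quantities.

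For readmissions and ED visits, only the date of asking differs. It matters because visits to other institutions are learned partly by contacting the subject. A later contact means longer recall and more time in which a subject may become unreachable. That affects the completeness of the primary outcome and of the data used to validate the DERRI.

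**Working it through.** No sample size, power or alpha figure is involved. The check maps each mark in Table 2 to its week and sets it beside the text.

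| Item | Table 2 | Text |
|---|---|---|
| Follow-up call, randomised arms | week 13 | about 5 weeks (8(f), Data collection) |
| Questionnaires and DKT2, randomised arms | weeks 0 and 13 | baseline and 5 weeks (8(e), outcomes 10 to 14; 8(f), Data collection) |
| Ascertainment of 30-day events, randomised arms | week 13 | about 5 weeks (8(f), Data collection) |
| Chart review, call and 30-day events, low-risk group | week 13 | about 5 weeks (8(f), Low-risk group) |
| Blood glucose, usual care | week 13 | about 5 weeks (8(f), Data collection) |
| Questionnaires and DKT2, low-risk group | weeks 0 and 13 | listed at baseline, absent from that group's follow-up list |
| Adverse events | intervention: 2 days to week 5; usual care: week 13 | no time stated for usual care |
| A1c | weeks 0 and 13 | baseline and 3 months: agrees |
| Navigator calls | 2 days, weeks 1 to 4 | 24 to 48 hours, then weekly for four weeks: agrees |
| Interview, intervention arm | week 5 | between one and two months: compatible |

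**Could this be a column shift in reading the PDF?** Each row checked has exactly eight cells after its label. Visit 7 is in use: the interview and the last intervention-arm glucose and adverse-event marks stand there. The A1c and Navigator rows agree with the text. A shift would have to move the same rows in all three groups and leave those in place. That is unlikely but not excluded.

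**Size of the gap**
- Week 5 is 5 × 7 = day 35, and week 13 is 13 × 7 = day 91.
- Shift: 91 − 35 = 56 days, or 8 weeks.
- Time since the last Navigator call (week 4): 5 − 4 = 1 week, against 13 − 4 = 9 weeks.
- Time from the close of the 30-day window to the contact: 35 − 30 = 5 days, against 91 − 30 = 61 days.

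**The case against.** The best reply is that the text already settles the matter. Outcomes 10 to 14 each state 5 weeks, two passages of section 8(f) state about 5 weeks, and section 8(a) ties payment to completion of 30 days of follow-up with outcomes assessed. The opposing evidence is the position of marks in a table read from a PDF, and that staff would follow the table is conjecture. This stands as a reason to check the source and to correct the table rather than the endpoint list. It does not remove the conflict, since a visit schedule is what staff normally work from.

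Four stronger readings are tempting, and the documents do not support them.

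- *A reader might infer that the primary outcome is contradictory.* It is not. The 30-day window is the same throughout, and only the date of ascertainment differs. Temple events come from the medical record whenever it is reviewed. The longer recall bears on visits elsewhere, mainly in subjects with no Temple event. The rule of contacting only those subjects is stated for the low-risk group; for the randomised arms the text simply combines phone interviews with record review.
- *A reader might take section 8(d) as a second contradiction.* A1c change is an outcome assessed at 3 months, so the sentence is correct as written. It does not say that all outcomes are assessed then.
- *A reader might say that the low-risk questionnaires are simply eight weeks late.* The low-risk follow-up list does not include them, so the first question for that group is whether they are repeated at all.
- *A reader might say that usual-care adverse events belong at week 5.* No text fixes their time. What the table shows is unequal timing between the arms.

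**Conclusion.** The point holds as an internal contradiction in the schedule. In the randomised arms, Table 2 would measure five secondary endpoints 8 weeks after their defined time and shows no follow-up call at week 5. In all groups it would ascertain 30-day events at about day 91 rather than day 35, lengthening recall of outside visits from about 5 to about 61 days past the window. The documents give no figure for how many visits would be missed or how many subjects lost in the added 8 weeks, so the effect on the readmission rate cannot be sized. The event definition and the sample size are unaffected.

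The conclusion assumes that the marks in the source PDF stand where they stand in the text version reviewed. It is worth correcting before use because the time point defines five endpoints and the correction is cheap.

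**What to change.** Check the marks against the source PDF. If they stand as read, then in Table 2:

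1. Move the follow-up call or chart review and the 30-day endpoint marks to visit 7 (week 5) in all three groups.
2. In the two randomised arms, move the follow-up marks for the questionnaires and diabetes knowledge to visit 7, and likewise the usual-care blood glucose mark.
3. Keep A1c at visit 8.

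Two items need a decision by the sponsor as well as an edit. Table 2 and the low-risk text must be reconciled on whether that group repeats the questionnaires and the knowledge test. The timing of adverse-event collection must be reconciled so that both randomised arms are assessed over the same period.

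Section 8(d) needs no correction; a note that the 3-month outcome is A1c is optional. The cost is a table edit and those two decisions. Moving the marks adds no visits.

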a) Recruitment Methods

We will recruit study subjects as follows:

1. We will review a daily computer-generated admission log of patients admitted to medical-surgical units at TUH who have been ordered for routine glucose testing. This captures most patients with recognized diabetes.
2. We will review the medical chart of patients on the admission log to determine potential eligibility. We request a waiver of consent and HIPAA to identify candidates. We will access only the minimum data needed to obtain this information.
3. We will request permission to approach the potential subject about the study from a physician on the primary team providing hospital care.
4. Study participants will be provided \$50 after 30 days of follow-up has been completed and outcomes have been assessed. Subjects who also provide an in-depth interview after the follow-up period will be given another \$50.

b) Inclusion and Exclusion Criteria

Screening for eligibility will be performed by chart review and brief history of the potential subject.

Inclusion criteria

1. Diabetes, defined by pre-admission use of a diabetes-specific medication and/or documentation of the diagnosis in the medical record.
2. Age 18 years or older at the time of admission
3. Admission to a non-critical care unit

Exclusion Criteria:

1. Female subjects who are pregnant and/or admitted to an obstetric service

Readmission Pilot Trial

2. Binge drinking (5 or more alcoholic drinks for males or 4 or more alcoholic drinks for females on the same day) or drug abuse within 3 months before admission
3. Receiving palliative care during the hospitalization
4. Participation in another readmission risk reduction program
5. Inpatient death
6. Planned or actual transfer to another hospital or subacute facility
7. Discharge to hospice or a long-term care facility
8. Discharge by signing out against medical advice
9. Discharge expected within 12 hours or admission to a short-stay unit
10. Lack of access to a phone
11. Living more than 30 miles away from TUH
12. Mental condition rendering the subject unable to understand the nature, scope, and possible consequences of the study
13. A1c <5.7%
14. Inability to speak English

c) Local Number of Subjects

Up to 300 subjects will be enrolled locally across the following study groups: 60 subjects in the intervention group, 60 in the high-risk control group, and 180 in the low-risk control group.

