Intervention protocol: The multifactorial intervention is based on strategies that reduced 30d readmissions in other populations, Temple’s successful readmission reduction program for heart failure patients (Temple Advantage), and the PI’s own preliminary studies. There are four components of the intervention: 1) patient-centered discharge education, 2) peri-discharge coordination of care, 3) A1c-based adjustment of diabetes therapy upon discharge, and 4) post-discharge support.

1) Patient-centered discharge education:

1a) *Standardized diabetes discharge instructions and education:* A Navigator will review instructions containing basic diet, activity, and diabetes-specific self-care guidance, as well as education on how to recognize and treat hypoglycemia and hyperglycemia (**Appendix Item 1**). These instructions are based on the model published by one of the PI’s mentors, [name], and others.[53] They also include a table that allows a provider to specify how and when insulin should be taken and discussion of the subject’s A1c level, of which many patients are not aware according to Preliminary studies. Lastly, patients who have not completed a formal diabetes education program in the past year will be referred to a Certified Diabetes Educator at the Temple Diabetes Center, an American Diabetes Association-certified outpatient diabetes education center.

1b) *Comprehensive discharge plan review:* Prior to discharge or soon after discharge, a Navigator will review the discharge plan with participants, including medications, reasons for and importance of follow-up appointments and testing, and how to reach post-hospital providers.

2) Peri-discharge coordination of care: Soon after discharge, a Navigator will assess and address barriers to following the discharge plan, including obtaining medications. A Navigator will confirm the scheduling of follow-up appointments and testing (including a visit with the primary care provider), help organize post-discharge services, assess barriers to keeping appointments, and confirm plans to attend follow-up appointments including transportation. In addition, a Navigator will assist subject with obtaining medications if needed. See **Appendix Item 2** for script.

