4) Post-discharge support: At 24 to 48 hours post-discharge, a nurse Navigator will call the patient to assess the patient’s status, confirm receipt of and compliance with medications, verify the follow-up appointment schedule, assess for barriers to following the discharge plan, determine the need for a community health worker (CHW) referral, and review blood glucose control (patients who are discharged on non-insulin regimens will be expected to test their blood glucoses at least once a day, and patients who are discharged on an insulin regimen will be expected to test their blood glucoses at least twice a day). Similar phone calls will be made weekly for four weeks following discharge by a Navigator. If a patient reports significant high or low blood glucose levels, then the PI or a co-Investigator (Endocrinologists) will call the patient to adjust diabetes therapy (See Tables 1a and 1b for insulin dose adjustment protocols). Eligible patients will receive a referral for a nursing visit from a local home care agency to assess medical needs for support at home and medication reconciliation. Referral to a CHW may be made if subjects are found to have non-medical needs and/or obstacles to maintaining self-care and attending follow-up appointments. Such non-medical support might include transportation to and from medical appointments, food, housing, or legal assistance, relief from utility bills, verification of insurance, support groups and delivery of durable medical equipment.

Table 1a. **Outpatient basal insulin dose adjustment:**

Basal Insulin	
If mean FBG > 180 mg/dL for the last 2 consecutive days and no episodes of hypoglycemia	Increase daily basal dose by 4 IU
If mean FBG > 140 mg/dL for the last 2 consecutive days and no episodes of hypoglycemia	Increase daily basal dose by 2 IU
If mean FBG between 100 to 140 mg/dL for the last 2 consecutive days and no episodes of hypoglycemia	No Change
If any FBG between 70 – 99 mg/dl	Decrease by 4 IU or 10% of total daily basal dose
If any FBG < 70 mg/dl	Decrease by 8 IU or 20% of total daily basal dose
If any FBG < 40 mg/dl	Decrease total daily basal dose by 30%

FBG=Fasting blood glucose; Hypoglycemia=typical symptoms (e.g., sweating, tremor, acute hunger, anxiety) and/or blood glucose <70 mg/dL

Table 1b. **Outpatient prandial/pre-meal insulin dose adjustment based on subsequent mealtime/HS BG values:**

Pre-meal Rapid Insulin		
Pre-meal Dose, U	BG 70 – 100 mg/dl*	BG 141-180 mg/dl**

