All data collected by the research team will be considered part of the participant's confidential record. Data collected on paper from research participants will be placed in a locked file cabinet in the GCRC within 24 hours. The destruction date of paper files will be at least 7 years from the termination of the study and will be authorized by the PI. Access to research and confidential records will be limited to clinical investigators and research coordinators.

h) Data Management

Statistical analysis: Distributions of the data will be assessed by descriptive statistical and graphical methods. To assess the randomization procedure, baseline values of all variables will be compared between the intervention and usual care group. Between-group differences for continuous variables will be compared using the Wilcoxon test. Proportions will be compared between groups using the chi-square test or exact tests when expected cell counts are less than 5. The primary outcome of 30d readmission rate will be compared between intervention and control groups with the chi-square test. Point estimates of 30d readmission rates will be obtained and presented with 95% confidence intervals. Time to readmission will be estimated by Kaplan-Meier curve and compared between groups by log-rank test. The composite of 30d readmission and ED visits will be compared by Cox regression model. Continuous secondary outcomes will be compared using Wilcoxon test. Categorical secondary outcomes will be compared using chi-square test. The primary analyses for all outcomes will be performed in the intention-to-treat (ITT) population. Secondary analyses for all outcomes will be performed in a per-protocol population restricted to subjects who complete at least one follow-up phone call. In addition, outcomes will be assessed for differences by the number of follow-up phone calls

Readmission Pilot Trial

completed (dose-response analysis). Lastly, all outcomes will be assessed in the ITT subgroup of subjects with a baseline A1c >7%. Statistical significance will be claimed at an alpha level of 0.05.

Power analysis: The sample size for Phase 2A was based on an expected drop-out and post-enrollment exclusion rate of 25% as well as the capacity of the research team. Because this is a pilot feasibility trial, the study is not powered to detect a difference in outcomes.

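### The 3-month A1c depends on routine care and a mailed letter, while the intervention supports attendance and testing, so A1c completeness may differ by arm and the comparison is at risk of selection bias

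*Protocol*

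**What the plan says.** Section 8 e) lists as secondary outcome 15 the "change in A1c level from baseline to 3 months after the index discharge". Table 2 lists A1C at baseline and at follow-up for all three groups.

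The Data collection text in Section 8 f), Phase A, says how the value is obtained: "Baseline and 3-month post-discharge A1c levels will be obtained as part of standard-of-care". The next sentence gives the prompt: "A letter reminding patients to do the 3-month blood draw for the A1c test will be sent by mail". The letter is not restricted by arm. No draw run by the study is described. The participant payment in Section 8 a) is due "after 30 days of follow-up has been completed and outcomes have been assessed", so it is not tied to the 3-month draw.

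Under peri-discharge coordination, the intervention provides: "A Navigator will confirm the scheduling of follow-up appointments and testing (including a visit with the primary care provider), help organize post-discharge services". Navigators also assess barriers to keeping appointments and confirm plans to attend, including transport. Under post-discharge support, after the first call at 24 to 48 hours, "Similar phone calls will be made weekly for four weeks following discharge by a Navigator". Referral to a community health worker (CHW), who can help with transport, is possible.

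Usual care has one CHW call at 2 to 4 days for most patients, which includes a check on follow-up appointments.

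Section 8 k) provides for permission to go on collecting medical-record data for intervention subjects and does not mention the usual-care arm.

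Section 8 h) sets the analysis: "Continuous secondary outcomes will be compared using Wilcoxon test". The primary analyses use the intention-to-treat population, and significance is claimed at 0.05.

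**The concern.** Randomisation protects the A1c comparison only if the subjects with a 3-month value are comparable between arms. Here the value is produced by routine care, and getting subjects to visits and tests is part of the randomised treatment. Visits scheduled and attended are themselves secondary outcome 4. Whether a value exists is therefore a post-randomisation event that treatment may influence. The withdrawal rule adds a second asymmetry, because medical-record review is one of the two stated sources of data.

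If measured usual-care subjects are a more self-selected group than measured intervention subjects, a difference in A1c change can appear or disappear without any effect on glycemia. An intention-to-treat label does not supply missing values, and a rank test cannot show which way selection acted.

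A1c change is the natural readout of the intervention's third component, A1c-based adjustment of therapy. The pilot is meant to inform a definitive trial, so a contrast that mixes treatment effect with who was measured could mislead that step. An analysis plan can adjust for missing A1c values but cannot recover values that were never collected.

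**Working it through.** The protocol states no A1c effect size, SD or completion rate, so there is no figure of its own to reproduce.

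**Inputs from the protocol.** 60 subjects per randomised arm (Section 8 c); 25% expected drop-out and post-enrollment exclusion, not split by arm and not specific to A1c (Section 8 h); Wilcoxon test at 0.05; last Navigator call at week 4; A1c at 3 months (week 13 in Table 2). The gap between the last call and the draw is 13 − 4 = 9 weeks. At 25% loss, 60 × 0.75 = 45 per arm remain.

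**Assumed inputs.** Completion rates by arm, the correlation rho between engagement and A1c change, and the SD of A1c change.

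**Illustration 1: normal selection model, no true effect.** A subject is measured if a latent engagement score is in the top share p.

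Bias in SD units = rho × [λ(p control) − λ(p intervention)], with λ(p) = φ(z)/p and z the cut-point for share p.

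λ(0.80) = 0.350, λ(0.75) = 0.424, λ(0.60) = 0.644, λ(0.50) = 0.798.

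For example, at 80% versus 50% and rho 0.4: 0.4 × (0.798 − 0.350) = 0.179 SD.

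The rejection rates come from simulating the Wilcoxon test with 60 randomised per arm, 4,000 trials per row.

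| Completion, intervention vs usual care | rho | Bias (SD) | Null rejection |
|---|---|---|---|
| 75% vs 60% | 0 | 0 | 4.8% |
| 75% vs 60% | 0.2 | 0.044 | 5.6% |
| 75% vs 60% | 0.4 | 0.088 | 7.2% |
| 80% vs 50% | 0 | 0 | 5.4% |
| 80% vs 50% | 0.2 | 0.090 | 6.5% |
| 80% vs 50% | 0.4 | 0.179 | 12.6% |

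The simulation error near 5% is about √(0.05 × 0.95/4000) = 0.3 percentage points, so 5.6% is barely distinguishable from 5%. For an assumed SD of 1.5 to 2.5 A1c points, 0.179 SD is 0.27 to 0.45 points.

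Equal completion is not a full safeguard. At 75% in both arms, with selection related to outcome in usual care only (rho 0.4), the bias is 0.4 × 0.424 = 0.17 SD and rejection is about 12%.

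**Illustration 2: two types of subject, no true effect.** Assume that half are engaged and half are not. Measurement is 80% (engaged) and 30% (not engaged) in usual care, and 85% and 60% in the intervention arm. Overall completion is then 0.40 + 0.15 = 55% versus 0.425 + 0.30 = 72.5%.

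- If engaged subjects change by −1.0 and the others by 0: usual care −0.40/0.55 = −0.727; intervention −0.425/0.725 = −0.586. The false difference is 0.14 points against the intervention.
- If the pattern is reversed (engaged 0, others −1.0): usual care −0.15/0.55 = −0.273; intervention −0.30/0.725 = −0.414. The false difference is 0.14 points in favour of the intervention.

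**Scale.** With 33 and 43.5 subjects measured, the standard error is SD × √(1/33 + 1/43.5) = 0.231 × SD, or 0.35 to 0.58 points for SD 1.5 to 2.5. A shift of 0.14 is then about 0.24 to 0.41 standard errors.

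**The case against.** A reader might go further and infer that the A1c comparison is biased, or that A1c is measured only when a subject happens to return for care. The documents do not support either.

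- **Bias is not shown.** Unequal completion does no harm by itself. With rho = 0 the bias is zero and the rejection rate stays near 5%, even at 80% versus 50%. The protocol gives no completion rates, and every input that produces a bias is assumed. This stands.
- **There is a common prompt.** The letter asks for the 3-month draw and is not limited to one arm, and A1C is scheduled for all groups. This stands, but a letter is a weak prompt beside an intervention that works on barriers and transport.
- **The timing is loose.** Navigator help with appointments and testing is described as peri-discharge, calls end about 9 weeks before the draw, and no Navigator prompt for the 3-month A1c is described. Carry-over is an inference. It is a plausible one, because some intervention-arm links reach further: study-supplied medication for those who cannot afford it, for the duration of the study; in-person interviews with about 20 subjects at one to two months; and referral for diabetes education, which usual care offers case by case.
- **Usual care has contact too.** The CHW call at 2 to 4 days checks follow-up appointments. It is one early call, for most patients.
- **The payment is the same in both arms.** It may explain missing values but not a difference between arms. This stands.
- **Missing-data methods and visit windows may be in the SAP,** which is not at hand. Their absence here is not counted as a fault.
- **The stakes are limited.** This is a secondary outcome in a pilot that the protocol says is not powered for outcome differences.

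**Conclusion.** The point holds as a risk, not as a demonstrated bias. The protocol obtains the 3-month A1c through standard of care with a mailed letter as the only stated prompt. It gives the intervention arm alone Navigator support for attendance and testing, and it states continued record collection for that arm alone. A1c completeness may therefore differ by arm. A bias follows only if being measured is also related to A1c change, and its direction and size cannot be determined from the protocol.

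Under the assumed rates in the table, the shift runs from 0 to 0.18 SD and null rejection from about 5% to 12.6%. The 0.14-point figure is an illustration under assumed inputs, and its sign reverses when the assumed pattern reverses. For comparison, with 45 per arm a difference of about 0.60 SD would be needed for 80% power, so the possible shift is small beside the trial's own imprecision. The primary 30-day readmission outcome is not affected. This is a worthwhile low-cost improvement rather than a threat to the trial's main result.

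**What to change.** 1. In the Data collection text of Section 8 f), keep the letter and add one reminder call near week 13 by the Research Specialist, identical in both randomised arms and separate from the Navigators. The draw stays standard of care.
2. In the same place, state that any A1c in the medical record or an outside record is captured by the same rule in both arms.
3. In Section 8 k), seek the same permission for continued medical-record collection after withdrawal in both arms.
4. Report the percentage with a 3-month A1c by arm, and add a sensitivity analysis of A1c change that accounts for missing values. If the SAP already specifies this, nothing more is needed.

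The cost is about 120 short calls (60 + 60) by existing staff and a little analysis work. The downside is one minor extra contact in usual care, after the 30-day endpoint. The call would not remove every effect of engagement on who is measured, so the completeness report is needed as well.
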